#### 5.1 Definition of Study Day

Study day will be calculated relative to the date of [Ga]-NeoBOMB1 administration as follows:

- Assessment/event date date of [Ga]-NeoBOMB1 administration + 1, if assessment/event date is on or after the date of [Ga]-NeoBOMB1 administration;
- Assessment date/event date date of [Ga]-NeoBOMB1 administration, if assessment/event date is before the date of [Ga]-NeoBOMB1 administration.

Note that under the convention specified above, there will be no Study Day 0.

#### 5.2 Baseline Definition

Baseline value for any given variable is defined as the last assessment obtained prior to the initiation of the [Ga]-NeoBOMB1 administration.

#### 5.3 Unscheduled Visits

In general, by-visit summaries will be presented by the scheduled visits (visit number and corresponding visit name of planned clinical encounter). Visit windowing will not be used for handling unscheduled visits. Instead, all unscheduled visits will be assigned a visit name of "Unscheduled". Such visits will be included in data listings and will contribute to the derivations of the best, worst, minimum, or maximum values where required.

#### 5.4 Handling of Missing Data

Missing/Partial Dates:

- In cases of incomplete dates (e.g. AEs and concomitant medications), the missing component(s) will be assumed as the most conservative value possible. No imputation of start/end dates or times will be performed.
  - If a medication date or time is missing or partially missing and it cannot be determined whether it was taken prior or concomitantly, it will be considered both a prior and a concomitant medication.
  - If the partial AE onset date/time information does not indicate that the event started prior to or after the treatment, the event will be classified as treatment-emergent.

- Time from first diagnosis of primary cancer (months) is calculated as (date of administration of the study drug date of first diagnosis + 1)/30.4375. If the month and year of the first diagnosis are provided but the day is missing, the missing day is imputed as 15. If only the year is provided, then the missing month and day are imputed as July 1st for the calculation.
- Actual data values as they appear in the original case report forms (CRFs) will be presented in the data listings.

Other Missing Values: Missing values for other individual data points will remain as missing unless otherwise specified. Missing values will not be imputed and only observed values will be used in data analyses and presentations unless otherwise stated.

#### 5.5 Multicenter Studies

The center effect will not be considered for this study.

#### 5.6 Multiple Comparisons/Multiplicity

No adjustment for multiplicity will be conducted.

#### 5.7 Other Data Handling Approaches

For continuous variables, the estimated mean, median, and quartiles for a set of values will be displayed to one more decimal place than that of the majority of the individual measurements, and the standard deviation will be printed out to 1 additional place. P-values will be given with 4 decimals (i.e., 0.xxxx). When a p-value is less than 0.0001, '<0.0001' will be displayed.

All fractional numeric values will be printed with a zero to the left of the decimal point (e.g., 0.12, 0.3 etc.). Percentage values will be printed with 1 digit to the right of the decimal point (e.g., 52.3%, 8.9% etc.).

#### 6 ANALYSIS OF DISPOSITION AND SUBJECT CHARACTERISTICS

#### 6.1 Subject Disposition and Analysis Populations

Subject disposition and analysis populations will be tabulated for each tumor type and in total when feasible. Otherwise, summary will be tabulated in total.

The number of screened subjects (the ones who sign the ICF) and the number of screen failures along with the primary reason of screen failure will be tabulated. Similarly, the number of subjects in the Full Analysis Set and the Per Protocol Set will be summarized.

The following subject disposition categories will be summarized for all enrolled subjects:

• Number of subjects who received the treatment and completed the study,

• Number of subjects who received the treatment but discontinued from the study.

For subjects who discontinued from the study, the primary reason for discontinuation will be summarized.

All deaths that occur during the study will be reported in a subject-level data listing, which will include subject demographics, dates of the IMP administration, cause of death, and the number of days between IMP administration and death.

All subject disposition data will be presented in data listings.

#### 6.2 **Protocol Deviations**

Protocol deviations will be captured in the study. The protocol deviation plan provides the definition of the protocol deviation in this study, for CSR reportable and CSR non-reportable.

Protocol deviations and violations will be reviewed and any subject data that will be excluded from the PP analyses due to major protocol violations will be determined prior to database lock.

#### 6.3 Demographics and Baseline Characteristics

Demographics and baseline characteristics will be summarized descriptively based on the Full Analysis Set for each tumor type and in total, and may be repeated on the PP Set if deemed appropriate.

Sex and race will be summarized by the number and percentage of subjects in each category. Age at informed consent (years), weight, height and body mass index (BMI) at baseline will be presented with summary statistics (n, mean, standard deviation, minimum, median, quartiles, and maximum).

Baseline disease characteristics will be summarized descriptively. Time from initial (first) diagnosis of primary disease (months) and time from initial (first) diagnosis of metastasis (months) will be summarized using descriptive statistics (n, mean, standard deviation, minimum, median, quartiles, and maximum). Diagnostic stage, diagnostic tumor stage, diagnostic node stage, and diagnostic metastasis stage will be summarized to show the number and percentage of subjects in each category.

Time from initial diagnosis of primary disease or metastasis will be calculated as follows:

(Date of IMP administration – Date of initial diagnosis + 1)/30.4375

Data listings of subject demographic and baseline disease characteristics will be provided.

#### 6.4 Prior and Concomitant Therapies/Medications

Prior and concomitant medications and cancer therapies/medications will be coded using WHO Drug. Prior and concomitant cancer surgeries, concomitant medical procedures/non-drug therapies will be coded using MedDRA. Dictionary versions will be updated biannually.

Prior medications, therapies, surgeries, or procedures are defined as those which started prior to the start of the IMP administration.

Concomitant medications, therapies, surgeries, or procedures are defined as those received by the subject on or after the start of IMP administration.

The following variables will be tabulated on FAS (for each tumor type and in total) to characterize the extent of prior cancer treatments:

- Prior cancer therapies/medications (yes, no);
- Number of prior cancer therapy/medication lines  $(0, 1-2, \ge 3)$ ;
- Number of prior cancer therapy/medication lines (as a continuous variable);
- Number of treatment cycles to the most recent prior therapy/medication line (as a continuous variable);
- Best response to the most recent prior cancer therapy/medication line (CR, PR, SD, PD, or Not Evaluable);
- Prior radiotherapy (yes, no); and
- Prior cancer-related surgery (yes, no).

The number and percentage of subjects treated with concomitant cancer therapy/medications, cancer surgery, medications, or medical procedures/non-drug therapies will be summarized based on FAS. Medications and cancer therapies/medications will be summarized by anatomic therapeutic class (ATC) and preferred term (PT) for each tumor type and in total. Cancer surgery and medical procedures/non-drug therapies will be similarly summarized by system organ class (SOC) and PT.

The subject data on all (prior and concomitant) cancer therapy/medications, radiotherapy, cancer surgery, medications, and medical procedures/non-drug therapies will be provided as data listings.

#### 6.5 Medical History

Medical history will be coded using MedDRA version available at the time (updated biannually). The number and percentage of subjects will be summarized by SOC and PT based on Full Analysis Set for each tumor type and in total.

All subject-level medical history data will be provided as data listings.

#### 6.6 Dosing

All study drug administration data will be listed by subject.

#### 7 ANALYSIS OF EFFICACY

Efficacy analyses will be performed primarily on the Full Analysis Set, but may be repeated on the PP Set if deemed appropriate. In general, the efficacy results will be presented overall, as well as split by tumor type and by GRPR positive and negative (if at least one GRPR-negative patient is enrolled).

#### 7.1 Number and Location of Lesions Identified by [Ga]-NeoBOMB1 by PET Imaging

The preliminary targeting properties of [Ga]-NeoBOMB1 will be assessed by summarizing the number and location of lesions identified by PET overall and split by GRPR positive and negative patients, as well as by tumor type.

The number and location of lesions identified by aforementioned PET imaging will be compared with the number and location of lesions identified by the comparable conventional imaging.

#### 7.2 Evaluation of Targeting Properties by Standard Uptake Value (SUV)

Targeting properties of [Ga]-NeoBOMB1 will also be evaluated by PET imaging using tumor uptake. Tumor uptake will be evaluated by the Standard Uptake Value (SUV) at each lesion by PET Imaging. The maximum SUVmean and SUVmax (g/mL) of each lesion will be presented by the lesion location with summary statistics (n, mean  $\pm$  standard deviation, minimum, median, quartiles, and maximum) at scheduled time points overall and split by GRPR positive and negative patients, as well as by tumor type. Dosimetry and non-dosimetry group will be summarized separately due to different scheduled time points.

The 80% and 95% confidence intervals for difference in SUV (SUVmean and SUVmax) between GRPR positive and negative patients will be derived by Student's *t* distribution if normality assumption is adequate, or Wilcoxon Rank Sum method otherwise.

The Standard Uptake Value ratio (SUVr) at each time point will be calculated as the SUVmean of each lesion / the SUVmean of different regions as a reference and presented in a data listing.

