## 7.4.1 Lesion-Level Analyses of Diagnostics by [Ga]-NeoBOMB1 Compared with Conventional Imaging

At lesion level, overall, positive, and negative agreement of [Ga]-NeoBOMB1 will be calculated based on the aforementioned tabulations as follows:

- Overall agreement = 100% x (Double positive + Double negative) / total number of patients who underwent both imaging procedures
- Positive agreement = 100% x Double positive / (Double positive + Comparator single positive)
- Negative agreement = 100% x Double negative / (Double negative + Comparator single negative)

The McNemars test may also be performed to assess the level of discordance between the two imaging techniques where appropriate, acknowledging issues with lack of independence of observations on a lesion level. The odds ratio and its confidence intervals (80% and 95%) will be computed for overall result and for each tumor type. The same calculation will be computed for GRPR positive and negative, if feasible.

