#### 7.5 Diagnostics by [Ga]-NeoBOMB1 Compared to Histological Evidence

The diagnostic performance of [Ga]-NeoBOMB1 to malignancies (lesions) known to overexpress GRPR will be compared with cytology and/or histopathology findings from archival and/or recent biopsy specimens.

Since the biopsy is only performed on one lesion, a direct link may not be possible if there are multiple lesions per organ identified on [Ga]-NeoBOMB1-PET. In this event, the determination of positive versus negative lesions on [Ga]-NeoBOMB1-PET will be done at organ level, i.e., if any lesion is positive in that organ, then the organ will be considered positive.

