#### 11 CHANGES FROM PROTOCOL-SPECIFIED STATISTICAL ANALYSES

The protocol did not specifically mention that SUVr would be calculated. SUVr will be derived by the statistics group and presented in a data listing.

Since the biopsy data only contains biopsies of one lesion per subject, comparison of the number of tumor lesions detected by [68Ga]-NeoBOMB1 with cytology and/or histopathology from archival and/or recent biopsy specimens will not be performed.

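### SAP 7.2 and 7.4.1 plan 80% and 95% intervals on lesion data without fixing the patient as the unit or adjusting for clustering; computed on lesions, they are too narrow when patients have several correlated lesions

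*SAP*

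**What the plan says.** **SUV difference (SAP 7.2).** The section sets the measurement at lesion level: "Tumor uptake will be evaluated by the Standard Uptake Value (SUV) at each lesion by PET Imaging". Summaries are by lesion location and scheduled time point, and "Dosimetry and non-dosimetry group will be summarized separately due to different scheduled time points". The next paragraph plans "The 80% and 95% confidence intervals for difference in SUV" between GRPR-positive and GRPR-negative patients, by Student's t "distribution if normality assumption is adequate, or Wilcoxon Rank Sum method otherwise". No mean, maximum or index-lesion rule turns the lesions of a patient into one value.

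**Odds ratio (SAP 7.4.1).** This section is explicitly lesion level. It allows a McNemar test, "acknowledging issues with lack of independence of observations on a lesion level", and then states: "The odds ratio and its confidence intervals (80% and 95%) will be computed for overall result and for each tumor type". No clustered method is named. Its overall agreement divides a count of lesions by a number of patients, so the unit is not used consistently there either.

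**Lesions per patient.** Eligibility (protocol 3.4.1) requires at least one lesion and sets no maximum. SAP 7.5 expects that "a direct link may not be possible if there are multiple lesions per organ identified".

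**GRPR status.** SAP 11 gives its reason for dropping one comparison as follows: "Since the biopsy data only contains biopsies of one lesion per subject". GRPR status is therefore in effect one value per patient.

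The general rules in SAP section 5 do not mention clustering.

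**The concern.** The t and rank-sum methods named in 7.2 assume independent observations. Lesions in one patient share the tumour, the injected activity, the scanner and the GRPR label, so their SUVs are likely to be positively correlated. Because GRPR status does not vary within a patient, all lesions of a patient fall on the same side of the comparison and the full design effect applies. Patients with many lesions also receive more weight.

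The 7.2 contrast addresses whether uptake follows receptor status. It belongs to the targeting properties that form the primary objective; protocol 7.3 lists SUV per lesion, split by GRPR status, under the primary endpoint. SAP section 5 presents comparisons of continuous variables through point estimates and confidence intervals, so the interval is the main inferential output. One labelled 95% that covers 80% would make a difference between GRPR groups look better established than it is. The 7.4.1 odds ratio, read as a comparison of the tracer with conventional imaging, carries the same risk.

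**Working it through.** **1. The plan's own precision figure.** SAP section 10 gives 66.4% to 92.7% for 25/30. The Wilson interval is [p + z²/2n ± z√(p(1−p)/n + z²/4n²)] / (1 + z²/n). With p = 0.8333, n = 30 and z = 1.96 it gives 66.4% to 92.7%, so the figure is reproduced. It is a patient-level figure and clustering does not touch it. The SAP gives no precision figure for lesion-level data.

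**2. Inputs for the SUV difference.**
- From the SAP: 50 patients; 30 GRPR-positive in the section 10 example; 80% and 95% levels.
- Assumed: 20 GRPR-negative (the remainder of 50); lesions per patient distributed as 1 + Poisson(m − 1) with mean m from 1 to 8; intraclass correlation ICC from 0.1 to 0.5.

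**3. Formula.** With unequal lesion counts the design effect is DE = 1 + (k − 1)·ICC, where k = E(count²)/E(count) = (m² + m − 1)/m. A lesion-level interval then covers 2Φ(z/√DE) − 1, with z = 1.96 (95%) or 1.2816 (80%).

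Example, m = 4 and ICC = 0.3: k = 19/4 = 4.75; DE = 1 + 3.75 × 0.3 = 2.125; √DE = 1.458; 1.96/1.458 = 1.345; coverage 82%.

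| Mean lesions m | ICC | k | DE | Coverage of 95% interval | Coverage of 80% interval |
|---|---|---|---|---|---|
| 1 | any | 1 | 1 | 95% | 80% |
| 1.5 | 0.1 | 1.83 | 1.08 | 94% | 78% |
| 1.5 | 0.5 | 1.83 | 1.42 | 90% | 72% |
| 2 | 0.1 | 2.5 | 1.15 | 93% | 77% |
| 2 | 0.3 | 2.5 | 1.45 | 90% | 71% |
| 4 | 0.1 | 4.75 | 1.38 | 91% | 73% |
| 4 | 0.3 | 4.75 | 2.13 | 82% | 62% |
| 4 | 0.5 | 4.75 | 2.88 | 75% | 55% |
| 8 | 0.5 | 8.88 | 4.94 | 62% | 44% |

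**4. Simulation check.** Normal data with no true difference, patient variance = ICC and residual variance = 1 − ICC, 30 versus 20 patients, at least 4,000 trials per setting. The pooled t interval on lesions agreed with the table to within one to two percentage points. The rank-sum interval (2,000 trials) gave nearly the same: 82% at (4, 0.3) and 64% at (8, 0.5).

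Analysing the dosimetry and non-dosimetry groups separately does not remove the loss. At (4, 0.3), a 24/16 split gave 83% and a 6/4 split 82%.

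A t interval on patient means covered 94–96% throughout. At 30/20 it was 1.16, 1.47 and 2.19 times as wide as the lesion-level interval at (2, 0.1), (4, 0.3) and (8, 0.5).

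**5. Odds ratio in 7.4.1.** The paired odds ratio is b/c, the ratio of the two discordant lesion counts. The SAP gives no interval formula, so a Wald interval on log(b/c) was assumed. Other assumptions: a mean of 4 conventional-imaging lesions per patient; 70% of them detected by the tracer (beta-binomial ICC 0, 0.1, 0.3, 0.5); 0.8 tracer-only lesions per patient (gamma frailty variance 0, 0.25, 1, 2). There were 10,000 trials per setting. The comparator was a patient-level linearised variance with a t reference on patients minus 1.

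| Clustering | Unadjusted 95%, 50 patients | Robust/Wald SE ratio, 50 patients | Unadjusted 95%, 10 patients |
|---|---|---|---|
| None | 96% | 0.98 | 96% |
| Weak | 93% | 1.08 | 94% |
| Moderate | 86% | 1.30 | 88% |
| Strong | 80% | 1.52 | 83% |

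The SE ratios account for the loss: 2Φ(1.96/1.30) − 1 = 87% and 2Φ(1.96/1.52) − 1 = 80%. The clustered interval covered 94.5–95% at 50 patients and 95–96% at 10. A percentile bootstrap over patients covered 92–94% at 50.

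**The case against.** - **7.2 may mean one value per patient.** It speaks of a difference between patients, so this reading is fair and the 7.2 problem is conditional. But mean, maximum and index lesion are different estimands and the SAP chooses none, so the unit needs stating on either reading. Section 7.4.1 allows no such reading.
- **7.4.1 already discloses the dependence.** It does, but only as a caveat to the McNemar test. A caveat does not widen the odds-ratio interval that follows.
- **The analyses are exploratory.** Section 5 says so of hypothesis testing, SUV itself is not among the primary endpoints in SAP 3.1, and primary-objective data are to be reported descriptively. This limits the consequence. It does not make a miscalibrated interval right.
- **The size is assumed.** This stands. The range includes no effect. If the 7.2 interval were taken within lesion location, fewer lesions per patient would enter: at a mean of 1.5 the loss is modest (94% to 90% for ICC 0.1 to 0.5). The odds-ratio results depend on further assumed detection rates and frailty variances.
- **There may be few GRPR-negative patients.** SAP section 7 allows for none. With few, imprecision dominates whatever the unit; with none, the 7.2 contrast falls away. Section 7.4.1 is affected either way.

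**Conclusion.** The concern holds. In 7.4.1 the lesion is plainly the unit and the planned intervals ignore clustering. In 7.2 the unit is unstated and the only SUV defined is per lesion. Computed on lesions, the intervals are too narrow if patients have several positively correlated lesions. With moderate assumptions (mean 4 lesions, ICC 0.3) a nominal 95% SUV interval covers about 82% and a nominal 80% interval about 62%. With one lesion per patient there is no loss. The true size depends on lesion counts and correlations that the documents do not give.

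The patient-level results in 7.4.2 and 7.5.2 are unaffected. The histology odds ratio in 7.5.1 is largely unaffected, because it rests on one biopsied lesion per subject. No decision rule uses the affected intervals, so this should be corrected but does not threaten the trial's conduct.

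**What to change.** **SAP 7.2.** State that the patient is the unit for the interval. At each scheduled time point, compute it on one value per patient, for example the mean SUV over that patient's lesions, and keep the t or rank-sum method. A mixed model with a random patient intercept and tumour type could be a sensitivity analysis if there are enough GRPR-negative patients.

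**SAP 7.4.1.** Replace the unadjusted odds-ratio interval, and any interval given for agreement, with a patient-clustered one: cluster-robust variance with a t reference on patients minus 1. A bootstrap over patients is an alternative for the overall result only. Label the by-tumour-type intervals, with 10 patients each, as small-sample.

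**Cost.** SAP wording and a little programming; no new data. SAP section 1 permits revision before database lock. The intervals become wider, those by tumour type stay imprecise, and patient means in 7.2 give patients with few and many lesions equal weight. The analyses remain exploratory.

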#### 7.3 Dosimetry and PK Analyses

Dosimetry calculations will be issued from the analyses of organs receiving the highest dose of [Ga]-NeoBOMB1, identified visually. Regions of Interest (ROIs) or Volumes of Interest (VOIs) will be placed over these organs to determine relative radiotracer uptake, calculated as a percentage of the injected dose per gram of tissue (%ID/g). Tissue time-activity curves with quantitative fractions of administered activity will be generated from the amount of radioactivity in one given tissue at a given moment over the amount of radioactivity present in the blood at that given moment and integrals will be calculated accordingly through dynamic acquisitions. Time activity curves ([TAC] - (u(t) in % injected dose per gram of tissue), describing %ID/ROI of the activity amount injected vs. time will be derived, considering renal excretion activity. Tissue activity curves will be fitted to mono- and bi-exponential curves to yield cumulative activities. Urine samples from 0-2h and from 2-4h post-injection will be collected to complete

dosimetry and biodistribution assessments. The absorbed dose ( $\mu$ Gy/MBq) will be transformed into formal biological equivalent dose for radiation exposure ( $\mu$ Sv/MBq) to finally yield an effective radiation dose, a factor between others that could help providing an estimation of total danger to the whole organism.

The absorbed dose in tumor and the effective radiation dose will be summarized with descriptive statistics (n, mean, standard deviation, minimum, median, quartiles, and maximum).

In addition, PK parameters such as  $C_{max}$ ,  $t_{max}$ , AUC(0-t), AUC(0-t)/D,  $t_{1/2}$ , AUC(0-inf), CL, Vd) will be listed and summarized using descriptive statistics.

Further details regarding Dosimetry calculations and analyses will be provided in a separate report by Rapid Dosimetry.

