### 4.1.7 Biodistribution and dosimetry

Sequential venous blood samples of 1 mL at baseline (immediately prior to injection, time 0) and at 5, 10, 20, 30±5, 1h±5min, 2h±10min and 3-4h±10min as well as 1ml-urine samples from the one produced over 0-2h and 2-4h after the end of infusion for dosimetric measurements will be collected.

Dosimetry calculations will be issued from the analyses of organs receiving the highest dose, identified visually. ROIs/VOIs will be placed over these organs to determine relative radiotracer uptake calculated as a percentage of the injected dose per gram of tissue (%ID/g). Tissue activity curves will be generated from the amount of radioactivity in one given tissue at a given moment over the amount of radioactivity present in the blood at that given moment and integrals will be calculated accordingly through dynamic acquisitions. Time activity curves ([TAC] - (u(t) in % injected dose per gram of tissue), describing %ID/ROI of the activity amount injected vs. time will be derived, considering renal excretion activity.

Tissue ACs will be fitted to mono- and bi-exponential curves to yield cumulative activities. Urine samples from 0-2h and from 2-4h post-injection will be collected to complete dosimetry and biodistribution assessments. The absorbed dose ( $\mu$ Gy/MBq) will be transformed into formal

biological equivalent dose for radiation exposure ( $\mu$ Sv/MBq) to finally yield an effective radiation dose, a factor between others that could help providing an estimation of total danger to the whole organism.

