### Secondary endpoints:

- The [68Ga]-NeoBOMB1 bio-distribution, pharmacokinetics, dosimetry and absorbed • dose in critical organs will be determined by calculation of TACs measured by a Nal gammacounter from blood and urine and stability will be analysed using HPLC measurements. Regions of interest (ROI) for critical organs and tumour lesions will be drawn using the acquired images resulting in time-activity curves with quantitative fractions of administered activity. Dosimetry calculations will be issued from the analyses of organs receiving the highest dose, identified visually. ROI will be placed over these organs to determine relative radiotracer uptake calculated as a percentage of the injected dose per gram of tissue (%ID/g). Tissue activity curves will be generated from the amount of radioactivity in one given tissue at a given moment considering renal excretion activity. Tissue ACs will be fitted to mono- and bi-exponential curves to yield cumulative activities. Urine samples 0-2h and 4h post-injection will be collected to complete dosimetry and biodistribution assessments. The absorbed dose (µGy/MBq) will be transformed into formal biological equivalent dose for radiation exposure (µSv/MBq) to finally yield an effective radiation dose, a factor between others that could help providing an estimation of total danger to the whole organism. Effective radiation dose will be summarized descriptively.
- Tumour uptake will be evaluated by Standard Uptake Value. SUVmean and SUVmax will be determined and summarized descriptively.
- Number of observed tumour lesions and localization in PET/CT will be summarized descriptively overall and split by GRPR positive and negative patients, as well as by tumour type, and will be compared to the number of observed lesions and localization in a comparable conventional imaging.
- Positive and negative lesions by the two imaging techniques will be cross tabulated overall and also by localization area on a lesion level and a patient level. This will also be repeated splitting by GRPR positive and negative patients and also by primary tumour type of patients in the trial.
  - On a lesion level overall, positive and negative agreement of [Ga]-NeoBOMB1 will be calculated as follows:
    - Overall agreement = 100% x (Double positive + Double negative) / total number of patients who underwent both imaging procedures

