#### 2.2 Trial Design

[figure not shown]
This is a Phase II, multi-center, open label, single dose study in patients with tumor types known to overexpress GRPR, including breast, prostate, colorectal, non-small cell and small-cell lung cancer.

Population will be divided in two groups:

• Phase-II dosimetry group: 10 patients bearing breast (n=5 female patients) and prostate cancer (n=5 male patients) will undergo additional assessments to confirm previous data on tracer bio-distribution, radiation dosimetry, residence time for critical organs, and absorbed dose critical organs for [Ga]-NeoBOMB1. Patients enrolled in the dosimetry group in France will be relapsed or refractory breast and prostate cancer. Serial venous whole blood and urine samples will be collected for activity-based pharmacokinetic characterization. Patients will undergo 4 15-min-static whole-body PET scans at 15 min, 1h±15 min, 2h±15 min and 4h±30 min post injection (p.i.) to determine absorbed doses to normal organs and to target tumor lesions. Venous whole blood samples will be collected at pre-dose (0), 5, 10, 20, 30±5, 60±5 min, and at 2h±10 min and 3-4 h±10 min p.i. Urine samples at pre-dose, from 0-2 h and from 2-4 h p.i. will also be collected.

• **Phase-II non-dosimetry group:** 40 patients bearing breast cancer (n=5), prostate cancer (n=5), colorectal cancer (n=10), NSCLC (n=10), SCLC (n=10). PET-imaging will be reduced to 2 whole body scans at 1h30±30min and at 2h30±30min likely to be a 15-min static late PET for all tumor-types. Only prostate tumor patients will undergo an additional early 5-min static PET scan to better assess lymph node metastases (if applicable). Blood and urine sampling will be omitted.

GRPR expression must be assessed while the study is ongoing within 4 weeks after IMP injection by Immunohistochemistry staining from archival or recent biopsy specimens (not older than 6 months prior to IMP injection).

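### SAP 7.3 and protocol 4.1.7 give two incompatible tissue time-activity curves (a tissue-to-blood ratio and %ID/ROI) and do not say which is fitted for cumulative activity; the ratio is not a valid input

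*SAP*

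**What the plan says.** SAP 7.3 sets out the dosimetry method in one paragraph, which contains two curves.

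- **Ratio curve.** Tissue time-activity curves are to be formed from the radioactivity in a tissue "over the amount of radioactivity present in the blood at that given moment and integrals will be calculated accordingly through dynamic acquisitions".
- **Percent-injected curve.** The next sentence derives time-activity curves "describing %ID/ROI of the activity amount injected vs. time will be derived, considering renal excretion activity". These have no blood denominator.
- **Fitting step.** "Tissue activity curves will be fitted to mono- and bi-exponential curves to yield cumulative activities". Nothing says which of the two curves is meant.

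Protocol 4.1.7 contains the same pair. Its ratio also takes tissue activity "over the amount of radioactivity present in the blood at that given moment", with the same reference to dynamic acquisitions, and it then describes the %ID/ROI curve.

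Other parts of the documents differ. Protocol 7.3, under secondary endpoints, reads: "Tissue activity curves will be generated from the amount of radioactivity in one given tissue at a given moment considering renal excretion activity". The synopsis row on data analysis, biodistribution and dosimetry also works from tissue activity alone, taken from static PET images.

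The scans are given in SAP 2.2: "Patients will undergo 4 15-min-static whole-body PET scans at 15 min", then at 1, 2 and 4 h. Protocol 4.2.2 and the schedules in protocol 4.5 agree. The non-dosimetry scans are also static. SAP 11, which records changes from the protocol's analyses, is silent on this point.

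**The concern.** Cumulated activity is the time integral of the actual activity in an organ or lesion, that is, with physical decay left in. Residence time is that integral divided by injected activity, and absorbed dose follows from it. A tissue-to-blood ratio is a contrast measure. It can rise while the activity in the tissue falls, and its integral does not count decays.

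The results at stake are named endpoints. SAP 3.1 places absorbed dose in tumour among the primary endpoints. SAP 3.2 lists residence times, absorbed doses in critical organs and effective dose as secondary. The dosimetry group of 10 patients exists to confirm earlier dosimetry, for which protocol 2.4 cites 0.026 mSv/MBq. That comparison needs a single, valid definition of the curve behind it.

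**Working it through.** The plan gives no figure of its own to reproduce here. The check is of definitions, followed by an illustration of size.

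**1. What the ratio retains.** Let A0 be injected activity, f the fraction taken up, and λp, λt and λb the physical, tissue-biological and blood-biological rate constants. With single exponentials:

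- Tissue activity: A_t(t) = A0 · f_t · exp(−(λp + λt)t)
- Blood activity: A_b(t) = A0 · f_b · exp(−(λp + λb)t)
- Ratio: R(t) = (f_t / f_b) · exp((λb − λt)t)

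Both A0 and λp have cancelled. If f_t and f_b are scaled together, R(t) does not change but the residence time does. With f_t = 2%, an assumed tissue biological half-life of 4 h and the 68-min physical half-life in protocol 5.1, residence time = f_t / (λp + λt) = 0.02 / (0.6116 + 0.1733) = 0.025 h. Scaling both fractions by 2 and by 5 gives 0.051 and 0.127 h, with the same ratio throughout. The ratio alone therefore does not determine cumulated activity, whatever half-lives hold.

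**2. Direction of the ratio.** The exponent of R is ln2 · (1/T_blood − 1/T_tissue). It is positive whenever blood clears faster than tissue. For assumed blood half-lives of 0.25, 0.5 and 1.0 h, combined with tissue half-lives of 2 h, 8 h and no biological clearance, all nine slopes are positive, from +0.35 to +2.77 per hour. In these cases a decaying exponential does not fit and the integral to infinity does not exist. With f_t = 5%, the tissue curve alone gives finite residence times of 0.052, 0.072 and 0.082 h for the three tissue half-lives.

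**3. Illustration of size.** The physical half-life is 68 min (protocol 5.1). The biological half-lives are assumptions that the documents do not give. Both curves are set to 1 at time zero.

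| Blood / tissue half-life (min) | 30 / 120 | 60 / 240 |
|---|---|---|
| Ratio exponent k = ln2(1/T_blood − 1/T_tissue), per min | 0.01733 | 0.00866 |
| Activity rate m = ln2(1/T_tissue + 1/68), per min | 0.01597 | 0.01308 |
| Rise in ratio, 15 to 240 min: exp(225k) | 49-fold | 7.0-fold |
| Activity left, 15 to 240 min: exp(−225m) | 2.8% | 5.3% |
| Ratio integral, 0-240 min: (exp(240k) − 1)/k | 63/0.01733 = 3636 | 7/0.00866 = 808 |
| Activity integral, 0-240 min: (1 − exp(−240m))/m | 61.3 | 73.1 |
| Quotient of the two integrals | 59.3 | 11.0 |

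**4. Feasibility as written.** Dynamic acquisitions are named as the route to the integrals, but none is scheduled. Blood is drawn at 10 and 20 min (SAP 2.2, protocol 4.1.7), so no sample is set for the start of the 15-min scan, although the ratio calls for blood at the same moment as tissue.

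**The case against.** The strongest reply is that a valid route already stands in the text. The sentence with the blood term itself calls the curves fractions of administered activity, which a tissue-to-blood ratio is not, so it contradicts itself rather than clearly prescribing the ratio. The sentence before it gives %ID/g and the sentence after it gives %ID/ROI. The synopsis takes the curves from static images. Protocol 3.3.2 and SAP 3.2 already list non-decay-corrected curves in organs and lesions. Further detail is left to a separate dosimetry report, and an experienced dosimetrist would probably pass over the ratio wording.

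Most of this stands, and it limits the point in four ways.

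- A reader might infer that the plan offers no valid way to reach absorbed dose. The documents do not support that: the %ID/ROI curve is a usable input.
- A reader might infer that reported doses will be wrong by a factor of 11 or 59. That is not supported either. Those factors assume that the ratio is the curve integrated, rest on half-lives outside the documents, and compare a dimensionless quantity with an activity through an arbitrary common starting value.
- No passage applies the ratio specifically to tumour. The region-of-interest text in SAP 7.3 concerns the organs with the highest dose, and the primary-endpoint text in protocol 7.3 has no blood term. The link to tumour dose is that SAP 7.3 reports it in the next paragraph and gives no other derivation.
- The missing 15-min blood sample could be bridged by interpolating between neighbouring samples, and tissue activity could be recovered by multiplying back by the blood curve. The plan states neither step.

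The reply does not remove the conflict. The report that would settle it is not available here, and SAP 7.3 presents it as adding detail, not as replacing the stated rule. The method for a primary endpoint should not depend on one of its own sentences being ignored.

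**Conclusion.** Wrong as written. SAP 7.3 and protocol 4.1.7 each hold two incompatible curve definitions and leave open which is fitted. One of them, the ratio, cannot give cumulated activity. It conflicts with the synopsis and protocol 7.3, and it relies on scans that are not scheduled. SAP 11 does not disclose the difference.

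That the ratio is not a valid input follows from the algebra and needs no assumed half-life. Divergence of its integral holds only where blood clears faster than tissue; elsewhere the integral is finite but still not cumulated activity. The factors of about 59 and 11 are illustrations under the stated assumptions, not estimates of error in this trial. Which curve will be used in practice cannot be told from these documents.

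**What to change.** In SAP 7.3 and protocol 4.1.7:

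1. Delete the blood denominator and the reference to dynamic acquisitions.
2. State that the curve fitted for cumulative activity, residence time and absorbed dose is the non-decay-corrected percent of injected activity in each organ or lesion, from the four static scans. This is already a listed endpoint in protocol 3.3.2 and SAP 3.2.
3. If a tissue-to-blood ratio is wanted, define it separately as a descriptive measure that does not enter the dose calculation.
4. Align the separate dosimetry report with this wording. If protocol 4.1.7 is left unamended, record the departure from it in SAP 11.

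The cost is about two sentences in each document, with no new data, scans or samples. SAP 1 allows revisions up to database lock.
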